3. CRITERIA AND DEFINITIONS USED IN THIS STUDY

3.1. Diagnostic Criteria for Advanced Hepatocellular Carcinoma

Patients who meet any of the following criteria will be considered to have advanced hepatocellular carcinoma.

- (1) Multiple hepatocellular carcinoma with at least 4 tumors
- (2) Hepatocellular carcinoma with vascular invasion
- (3) Hepatocellular carcinoma with extrahepatic spread that does not affect the prognosis

3.2. Tumor Assessment

Tumor response will be assessed using version 1.0 of the modified RECIST criteria (mRECIST) [1]. Assessments will be made based on changes in the diameter of surviving tumors deemed viable by a modality such as contrast CT that are observed until

completion or discontinuation of the protocol treatment.

At the time of enrollment for this study (before treatment), the 5 largest tumors among intrahepatic lesions with a large maximum diameter will be selected as target lesions. Lesions other than the target lesions will be included as non-target lesions, and the largest 5 of those will be selected and evaluated.

However, observation of a new intrahepatic lesion will not be considered PD in this study. Determinations of the best overall response will not require confirmation.

Table 2 Assessment of Target Lesion Response: Conventional RECIST and mRECIST Assessment for HCC Following the AASLD-JNCI Guideline

RECIST	mRECIST for HCC
CR = Disappearance of all target lesions	CR = Disappearance of any intratumoral arterial enhancement in all target lesions
PR = At least a 30% decrease in the sum of diameters of target lesions, taking as reference the baseline sum of the diameters of target lesions	PR = At least a 30% decrease in the sum of diameters of viable (enhancement in the arterial phase) target lesions, taking as reference the baseline sum of the diameters of target lesions
SD = Any cases that do not qualify for either partial response or progressive disease	SD = Any cases that do not qualify for either partial response or progressive disease
PD = An increase of at least 20% in the sum of the diameters of target lesions, taking as reference the smallest sum of the diameters of target lesions recorded since treatment started	PD = An increase of at least 20% in the sum of the diameters of viable (enhancing) target lesions, taking as reference the smallest sum of the diameters of viable (enhancing) target lesions recorded since treatment started

AASLD, American Association for the Study of Liver Diseases; JNCI, Journal of the National Cancer Institute; HCC, hepatocellular carcinoma; mRECIST, modified Response Evaluation Criteria in Solid Tumors; CR, complete response; PR, partial response; SD, stable disease; PD, progressive disease.

Table 3 Overall Response Assessment in mRECIST: Responses for All Possible Combinations of Tumor Responses in Target and Nontarget Lesions with or without the Appearance of New Lesions

Target Lesions	Nontarget Lesions	New Lesions	Overall Response
CR	CR	No	CR
CR	IR/SD	No	PR
PR	Non-PD	No	PR
SD	Non-PD	No	SD
PD	Any	Yes or no	PD
Any	PD	Yes or no	PD
Any	Any	Yes	PD

mRECIST, modified Response Evaluation Criteria in Solid Tumors; CR, complete response; PR, partial response; IR, incomplete response; SD, stable disease; PD, progressive disease.

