0.5. Treatments

0.5.1. Combination therapy with low-dose FP and sorafenib

Low-dose cisplatin will be administered on day 1, and fluorouracil will be administered by hepatic infusion using a reservoir for 5 days from day 1 through day 5, followed by 2 days off. This sequence will be repeated for 2 weeks, followed by 2 weeks off. Sorafenib will be administered continuously at a dose of 400 mg twice daily for 28 days from day 1 to day 28. This 4-week period constitutes one cycle, and cycles will be repeated until discontinuation of the protocol treatment. The first cycle of treatment will be started within 28 days of randomization. Earlier treatment with sorafenib will be allowed. However, patients must be off sorafenib for 2 days before and 7 days after reservoir placement. The next cycle of treatment will be started within 14 days. However, sorafenib will be continued during that time. This combination therapy will be repeated until progressive disease (PD) according to the modified RECIST criteria is documented [1]. (However, observation of a new intrahepatic lesion will not be considered PD.)

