2.3 Rationale for Treatment Plans

As explained above, it would be desirable to develop new effective drugs and treatment methods for hepatocellular carcinoma due to the high prevalence of the disease, the absence of effective treatments, and need for curative treatment, prevention of recurrence, and improved overall survival.

In Japan, hepatic arterial infusion chemotherapy is selected for patients with advanced hepatocellular carcinoma who are not candidates for surgical resection, local ablation therapy, or transcatheter arterial chemoembolization. However, the disease commonly begins to progress again even after the treatment shrinks the tumor, and the cancer recurs or the tumor starts growing again. Thus, treatment is often repeated as long as liver function will allow. Because of these issues, it would be desirable to develop a more effective treatment for this disease. Various multidrug therapies have been attempted to that end. The efficacy of low-dose cisplatin/fluorouracil hepatic arterial infusion chemotherapy has been demonstrated in large groups of patients with advanced hepatocellular carcinoma. However, sorafenib is the only drug demonstrated to increase the overall survival rate in patients with incurable advanced hepatocellular carcinoma in a clinical trial, and is hoped to be effective in clinical practice. The combination of two different types of treatment, specifically, hepatic arterial infusion chemotherapy and sorafenib, is hoped to better suppress recurrence and regrowth of hepatocellular carcinoma, and determining whether it can truly do so would be highly clinically significant. Therefore, this study was designed to assess the additive effects of low-dose cisplatin/fluorouracil hepatic arterial infusion chemotherapy on the current standard therapy of sorafenib monotherapy and to establish this new therapy as the standard therapy for this patient population. If this study demonstrates the clinical effectiveness of the treatment, it will be the

first time that the clinical effectiveness of hepatic arterial infusion chemotherapy (low-dose FP) is objectively demonstrated in a prospective comparative study.

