***Notes regarding discontinuation of the protocol treatment**

The protocol treatment should be continued for as long as possible by reducing doses and interrupting treatment as appropriate. If discontinuation is being considered after a dose reduction or during treatment interruption, the study coordinator or study chair should be promptly notified using the designated fax form. Whether to discontinue the protocol treatment will be determined upon discussion with the study chair. It is particularly important to promptly consult the study chair when considering discontinuation for a patient who does not meet the above criteria for discontinuation of the protocol treatment. However, it is acceptable to not follow this procedure if emergency discontinuation is required for safety reasons.

Contact information:

Study chair: [name], Department of Gastroenterology and Hepatology, Kindai University Faculty of Medicine

[contact] ([name])

[contact]

E-mail: [contact]

Study coordinator: [name], Department of Gastroenterology and Hepatology, Kindai University Faculty of Medicine

[contact] ([name])

[contact]

E-mail: [contact]

**The protocol treatment should generally be discontinued if the patient shows PD according to the modified RECIST criteria during the protocol treatment period. However, continuation of the protocol treatment is allowed if the investigator determines that the patient is responding clinically to the protocol treatment. It should be noted that observation of a new hepatic lesion is not considered PD in this study, and protocol treatment should be continued in these patients.

***The protocol treatment should be discontinued if the patient shows a CR according to the modified RECIST criteria. If recurrence is detected, appropriate treatment will be provided at that time. Treatment during this time will follow Section 6.5. Post-trial Treatment.

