21.4. Modified RECIST

Observation of a new intrahepatic lesion will not be considered PD.

Table 2 Assessment of Target Lesion Response: Conventional RECIST and mRECIST Assessment for HCC Following the AASLD-JNCI Guideline

RECIST	mRECIST for HCC
CR = Disappearance of all target lesions	CR = Disappearance of any intratumoral arterial enhancement in all target lesions
PR = At least a 30% decrease in the sum of diameters of target lesions, taking as reference the baseline sum of the diameters of target lesions	PR = At least a 30% decrease in the sum of diameters of viable (enhancement in the arterial phase) target lesions, taking as reference the baseline sum of the diameters of target lesions
SD = Any cases that do not qualify for either partial response or progressive disease	SD = Any cases that do not qualify for either partial response or progressive disease
PD = An increase of at least 20% in the sum of the diameters of target lesions, taking as reference the smallest sum of the diameters of target lesions recorded since treatment started	PD = An increase of at least 20% in the sum of the diameters of viable (enhancing) target lesions, taking as reference the smallest sum of the diameters of viable (enhancing) target lesions recorded since treatment started

AASLD, American Association for the Study of Liver Diseases; JNCI, Journal of the National Cancer Institute; HCC, hepatocellular carcinoma; mRECIST, modified Response Evaluation Criteria in Solid Tumors; CR, complete response; PR, partial response; SD, stable disease; PD, progressive disease.

Table 3 Overall Response Assessment in mRECIST: Responses for All Possible Combinations of Tumor Responses in Target and Nontarget Lesions with or without the Appearance of New Lesions

Target Lesions	Nontarget Lesions	New Lesions	Overall Response
CR	CR	No	CR
CR	IR/SD	No	PR
PR	Non-PD	No	PR
SD	Non-PD	No	SD
PD	Any	Yes or no	PD
Any	PD	Yes or no	PD
Any	Any	Yes	PD

mRECIST, modified Response Evaluation Criteria in Solid Tumors; CR, complete response; PR, partial response; IR, incomplete response; SD, stable disease; PD, progressive disease.

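### The response table still makes any new lesion PD while the protocol says a new intrahepatic lesion is not PD, so six response combinations have no consistent coding for TTP, ORR and OS by response

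*Protocol*

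**What the plan says.** **The rule.** Protocol 0.5.1 says for the combination arm: "However, observation of a new intrahepatic lesion will not be considered PD". Section 0.5.2 says the same for monotherapy, so the rule is the same in both arms. Section 3.2 repeats it: "However, observation of a new intrahepatic lesion will not be considered PD in this study". The notes to 6.2 say that "observation of a new hepatic lesion is not considered PD in this study, and protocol treatment should be continued in these patients". Section 21.4 has it once more, above the response table: "Observation of a new intrahepatic lesion will not be considered PD".

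**The table.** The overall-response table in 3.2 and again in 21.4 is the published mRECIST table, without adaptation. Its CR, PR and SD rows all carry No in the new-lesion column. Its last row turns any target status and any non-target status into PD once a new lesion is present. No row separates intrahepatic from extrahepatic new lesions.

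**Target lesions.** They are chosen once: "At the time of enrollment for this study (before treatment), the 5 largest tumors among intrahepatic lesions". A tumor that appears later never enters the sum of diameters.

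**Endpoints (11.6.2).** TTP and ORR are defined by modified RECIST, and TTP also has a date rule for clinical progression. PFS runs to a diagnosis of recurrence or to death. OS is compared between responders and non-responders.

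**Treatment (6.2).** CR is a criterion for discontinuation: "The protocol treatment should be discontinued if the patient shows a CR according to the modified RECIST criteria". The same notes say to continue when a new hepatic lesion is seen.

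**Rationale (2.3).** The combination "is hoped to better suppress recurrence and regrowth of hepatocellular carcinoma, and determining whether it can truly do so" is presented there as an important clinical question.

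**The concern.** The rule and the table cannot both be applied to a patient whose existing lesions are not progressing but who has a new liver tumor. Two assessors who each follow the protocol can code the same scan differently: one as PD from the table, the other as something else from the rule. The second assessor has no row to use.

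The protocol has few checks on this. The trial is open-label, best response needs no confirmation (3.2), the investigator's evaluation sets the progression date (11.6.2), and central reading covers only enrollment and the end of protocol treatment (11.2).

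What is at stake is the meaning of TTP, ORR and OS by response. PFS adds a further uncertainty, because its event is worded as recurrence and nothing says whether a new intrahepatic lesion is one. The added treatment is infused into the hepatic artery, so new liver tumors are a form of recurrence on which the arms might well differ.

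**Working it through.** **Step 1. Enumerate the table.** Inputs from 3.2: target status CR, PR, SD or PD (4); non-target status CR, IR/SD or PD (3); new lesion yes or no (2). That gives 4 × 3 × 2 = 24 combinations, of which 12 have a new lesion.

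- All 12 combinations without a new lesion match a row.
- Of the 12 with a new lesion, 3 have target PD and 3 more have non-target PD without target PD. These 6 are PD whatever the new lesion is.
- The other 3 × 2 = 6 match only the last row of the table.

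| Target | Non-target | New liver lesion | By the table | Under the rule | If scored on the other two columns |
|---|---|---|---|---|---|
| CR | CR | Yes | PD | no row | CR |
| CR | IR/SD | Yes | PD | no row | PR |
| PR | CR | Yes | PD | no row | PR |
| PR | IR/SD | Yes | PD | no row | PR |
| SD | CR | Yes | PD | no row | SD |
| SD | IR/SD | Yes | PD | no row | SD |

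The last column requires reading Yes as No. The protocol does not tell anyone to do that, but it offers no other category either.

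**Step 2. Follow the coding into the endpoints.**

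- *TTP:* an event by the table, no event by the rule, unless the investigator declares clinical progression.
- *ORR and OS by response:* four of the six combinations (one CR, three PR) would count as responders on the last column and as PD by the table.
- *PFS:* undetermined, because recurrence is not tied to mRECIST PD or to the rule. The same lesion could be a PFS event and not a TTP event.
- *OS:* death from any cause, so no dependence on the rule.
- *6.2:* a patient coded CR with a new hepatic lesion would meet both the note to stop and the note to continue. This arises only if that patient is coded CR.

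**Step 3. Direction of the effect on TTP (illustration only).** The documents give no rate of progression by new liver lesion alone. Assume that it is a share q of the control arm's progression hazard, that hazards are proportional, and that the two routes are independent. Then HR(all progression) = q × HR(new liver) + (1 − q) × HR(other), while TTP under the rule records HR(other).

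| q (assumed) | HR(new liver) 0.5, HR(other) 1.0: all / recorded | HR(new liver) 1.0, HR(other) 0.6: all / recorded |
|---|---|---|
| 0.2 | 0.90 / 1.0 | 0.68 / 0.6 |
| 0.3 | 0.85 / 1.0 | 0.72 / 0.6 |
| 0.5 | 0.75 / 1.0 | 0.80 / 0.6 |

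The recorded TTP hazard ratio can understate or overstate the effect on all progression. Using the rule in both arms does not remove this if the arms differ in new liver lesions.

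**Step 4. Scale for ORR (illustration only).** Phase I reported 7 PR among 18 patients, or 38.9% (2.4.3). In an arm of 95 that is 0.389 × 95 = 37 responders. If 10% of them (assumed) owed their response to a scan that also showed a new liver tumor, that is 3.7 patients, or 3.7 / 95 = 3.9 percentage points in that arm.

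**The case against.** The exception is deliberate. It is stated five times and applies to both arms, and preferring unmodified mRECIST would be a matter of taste. That stands: the exception is not the error. The error is that the table printed with it says the opposite.

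Four stronger readings are tempting, and the documents do not support them.

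- *Patients with new liver tumors are to be scored PR or CR.* No passage says so. Every CR, PR and SD row requires no new lesion. Such coding is possible, not prescribed.
- *TTP and ORR can show nothing about the hoped-for effect.* TTP still captures regrowth of target and non-target lesions, new extrahepatic lesions and clinical progression. Only new intrahepatic recurrence is lost, and only in imaging-based TTP under the rule. ORR does not measure recurrence under any rule.
- *Section 6.2 gives outright opposite orders.* If CR is read from the printed table, a patient with a new lesion is not CR and the stop note is not triggered. The conflict is conditional on the coding.
- *The trial's main question is compromised.* Recurrence and regrowth appear in the rationale, not as an endpoint. The objective is superiority in OS.

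Two further limits are fair. Because response needs no confirmation, a patient already PR before the new lesion appears stays a responder either way, so ORR changes only through new lesions present by the first responding scan. A supportive analysis may also sit in a statistical analysis plan that is not shown. It is offered here as part of the remedy; its absence from the protocol is not a finding.

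**Conclusion.** The point holds as an internal contradiction affecting secondary endpoints. Six of the 24 response combinations are PD by the table and uncategorised under the rule when the new lesion is intrahepatic. Four of the six could enter ORR and OS by response as responders. TTP depends on which text is followed, and PFS is undefined on this point. OS and the sample size built on it are untouched.

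The size cannot be derived from the documents. The shares and hazard ratios in Step 3 and the 10% in Step 4 are assumptions. The phase I rate comes from 18 patients on the combination and says nothing about the difference between arms. The enumeration needs no assumption beyond the printed table.

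This should be corrected, but it does not threaten the primary comparison.

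**What to change.** 1. Adapt the overall-response table in 3.2 and 21.4. For endpoint scoring, state the overall response of a patient with a new intrahepatic lesion, and do not count a scan showing a new viable intrahepatic lesion as an objective response.
2. State in 11.6.2 whether a new intrahepatic lesion is a PFS event.
3. Record the date of the first new intrahepatic lesion, if the existing forms do not already capture it. Report TTP, PFS and ORR under unmodified mRECIST as a supportive analysis beside the study definition.
4. Reconcile the passages in 6.2 on stopping for CR and on continuing with a new hepatic lesion, for a patient to whom both could apply. Item 1 concerns endpoint scoring only and is not meant to settle this. Which instruction applies is a clinical decision for the protocol's authors.

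The cost is at most one data field, some table rows and a small supportive analysis of scans already scheduled in 8.5. ORR may come out slightly lower. The exception for treatment decisions can stay as it is.

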3.3. Child-Pugh Score

	Point score calculated from observations		
	1	2	3
Grade of encephalopathy ^a	Absent	1-2	3-4
Ascites	Absent	Slight	Moderate
Serum bilirubin (mg/dL)	< 2	2-3	> 3.0
	(mcmol/L)	< 34	34-50
Serum albumin (g/dL)	> 3.5	2.8-3.5	< 2.8
INR	< 1.7	1.7-2.3	> 2.3
Prothrombin time (sec above normal)	< 4	4-6	> 6
Increase in prothrombin time (%)	> 70	40-70	< 40

a Grade of encephalopathy:

Grade 0: Lucid, normal personality, normal neurological test results, normal electroencephalogram

Grade 1: Restlessness, sleep disorder, irritability/agitation, tremors, dysgraphia, 5 cps waves

Grade 2: Lethargy, disorientation (temporal), inappropriateness, difficulty maintaining stable posture, ataxia, slow triphasic waves

Grade 3: Somnolence, confusional state, disorientation (spatial), hyperreflexia, rigidity, slow waves

Grade 4: Coma, no personality/unresponsive, cessation of cerebral activity, slow 2–3 cps delta activity

A: 5–6 points, B: 7–9 points, C: 10–15 points

*Ascites: Patients with a history of ascites who are currently using a diuretic are allotted 2 points even if they do not have ascites.

*Encephalopathy: Patients with a history of hepatic encephalopathy who are using a drug to treat encephalopathy are allotted 2 points even if they are asymptomatic.

3.4. Eastern Cooperative Oncology Group Performance Status (PS)

Grade	Definition
0	Fully active, able to carry on all pre-disease performance without restriction.
1	Restricted in physically strenuous activity, but ambulatory and able to carry out work of a light or sedentary nature (e.g., light house work or office work).
2	Ambulatory and capable of all selfcare but unable to carry out any work activities. Up and about more than 50% of waking hours.
3	Capable of only limited selfcare, confined to bed or chair more than 50% of waking hours.
4	Completely disabled. Cannot carry on any selfcare. Totally confined to bed or chair.

3.5. Staging by the General Rules for the Clinical and Pathological Study of Primary Liver Cancer

The overall stage of a cancer will be determined by calculating the stages for each component and selecting the highest one.

[figure not shown]
[figure not shown]

[figure not shown]
[figure not shown]
[figure not shown]

The overall stage will be determined from the following four components.

Stages of hepatocellular carcinoma

	T component	N component	M component
Stage I	T1	N0	M0
Stage II	T2	N0	M0
Stage III	T3	N0	M0
Stage IVA	T4	N0	M0
	T1, T2, T3, T4	N1	M0
Stage IVB	T1, T2, T3, T4	N0, N1	M1

T component: Determined from three factors: the number, size, and vascular invasion of tumors. Multiple tumors can be multicentric tumors or intrahepatic metastases. An S3 ruptured hepatocellular carcinoma is classified as T4.

T component of hepatocellular carcinoma

	T1	T2	T3	T4
(1) Number of tumors: Single	Meets all (1) (2) (3)	Meets 2	Meets 1	Meets none
(2) Tumor diameter: ≤ 2 cm				
(3) No vascular invasion (Vp0, Vv0, B0)				

N component:

N0: No lymph node metastasis

N1: Lymph node metastasis

M component:

M0: No extrahepatic spread

M1: Extrahepatic spread

4. CRITERIA FOR PATIENT SELECTION

This study will enroll patients with hepatocellular carcinoma who are not candidates for surgical resection, local ablation therapy, or transcatheter arterial chemoembolization. Patients must sign the informed consent form, meet all the inclusion criteria, and not meet any of the exclusion criteria. Before patient enrollment, investigators will collect all information about prescription of the study drugs and will familiarize themselves with safety information in the package inserts.

4.1. Inclusion Criteria

Patients who meet all of the following criteria in screening tests and observations within 28 days before enrollment will be included in the study.

- 1) At least 20 years of age (male or female)
- 2) Life expectancy of at least 12 weeks
- 3) Advanced hepatocellular carcinoma diagnosed as typical hepatocellular carcinoma histologically, cytologically, or by diagnostic imaging such as dynamic CT (MDCT), dynamic MRI, or CTHA/CTAP

*Patients who meet any of the following criteria are considered to have advanced hepatocellular carcinoma.

- (1) Multiple hepatocellular carcinoma with at least 4 tumors
 - (2) Hepatocellular carcinoma with vascular invasion
 - (3) Hepatocellular carcinoma with extrahepatic spread that does not affect the prognosis
- 4) Not a candidate for complete resection by hepatectomy, local ablation therapy, or transcatheter arterial chemoembolization, or is unlikely to respond to those treatments
 - 5) ECOG performance status (PS) of 0 or 1
 - 6) Child-Pugh score of 7 or lower (PT calculated as INR)
 - 7) Laboratory test values are within the prescribed ranges below. Patients can be re-tested during the screening period within 28 days before enrollment.
 - a) Hemoglobin \geq 8.5 g/dL
 - b) Neutrophil count \geq 1,500/ μ L
 - c) Platelet count \geq 50,000/ μ L
 - d) PT-INR \leq 2.3
 - e) Total bilirubin \leq 2 mg/dL
 - f) ALT and AST \leq 6 times the institutional upper limit of normal
 - g) Serum creatinine \leq 1.5 times the institutional upper limit of normal
 - h) Amylase \leq 2 times the institutional upper limit of normal

- 8) Provided written informed consent to participate in the study

